#### 1.4 BENEFIT - RISK ASSESSMENT

Based on available non-clinical data and based on clinical data from other compounds with a comparable mode of action BI 836880 is assessed to be generally safe for IVT use in humans ([c21397543](#)).

This is the first study using an IVT route of administration for this compound. However, IVT administration of an antibody that simultaneously binds to VEGF and ANG2 (faricimab, previously referred to as bispecific antibody RG7716) for treatment of wAMD has previously been tested in humans in a Phase 1 clinical trial [[R18-0309](#)], and a Phase 2 clinical trial [[R21-0692](#)]. In the Phase 1 trial, the co-administration of RG7716 was reported to be well tolerated and to exhibit a favourable safety profile overall [[R18-0309](#)]. In addition, there was preliminary evidence of improvements in BCVA and anatomic parameters for this mode of

action. In the Phase 2 trial, faricimab maintained vision and anatomic improvements comparable with SoC in wAMD in treatment naïve patients, resulting in the start of Phase 3 trials. These data support that the combination of anti-VEGF and anti-ANG2 can be used safely in patients with wAMD.

BI recommends the use of material for intraocular drug delivery, which is according to standard medical practice. This material is not officially approved for intraocular drug delivery, with associated potential risks. Long-term experience as standard of medical care suggests a favorable risk-benefit profile. To the best of the sponsor's knowledge there is currently no product on the market, which is officially approved for intravitreal drug delivery.

The needles for preparation of the drug and intravitreal injection are usually silicone oil coated to ease the injection of the needle through the tissue. This carries the potential risk for a silicone oil transfer into the vitreous with the potential risks for occurrence of side effects like vitreous floaters or intraocular inflammation. The overall risk for such events is based on long-term experience with comparable material and is considered low. However, patients should be made aware of this risk, as reflected in the Informed Consent Form (ICF). To the best of the sponsor's knowledge, there is currently no product on the market, which is silicone-free. The recommended syringes are silicone-oil-free and not considered to carry this risk. The IMP handling instructions do not mandate the use of materials from certain manufacturers and leave the decision to the treating investigators/sites on which material to use if it meets the specifications as described in the IMP handling instructions for BI 836880.

This trial will include in the SRD part and MRD cohort 1 patients with an insufficient response to the standard treatment for wAMD (IVT anti-VEGF therapy). Therefore, although this is a newly developed drug at an early stage of testing and an individual benefit cannot be guaranteed, trial treatment may result in an individual benefit to the individual patient. In addition, due to the long duration of the disease the patient may directly benefit from the drug development based on the results of this trial.

For the MRD cohort 2, treatment-naïve patients will be included based on a positive safety assessment as confirmed by the Safety Monitoring Committee (SMC), after three patients of MRD cohort 1 reach Visit 5, i.e. 4 weeks after the third injection.

For MRD cohort 3, frequently treated patients will be included (defined as patients receiving anti-VEGF every 4-8 weeks on average). These frequently treated patients are the intended final target population for BI 836880, because of the remaining unmet medical need for these patients to receive a higher potency anti-VEGF therapy. BI 836880 has shown potential efficacy signals in pretreated patients in the SRD/MRD part of the study and could therefore have a role in the treatment of patients needing frequent anti-VEGF therapy.

The following safety measures have been implemented to mitigate the risk and ensure early detection of intraocular inflammation (IOI): fluorescein angiography (FA) imaging will be required at screening and wide-angle fundus photography with a vitreous haze assessment will be required at every visit. Reports of IOI will be treated as an AE of special interest (AESI), see also [Section 5.2.8.1.4](#).

Furthermore, although rare, a potential for drug-induced liver injury (DILI) is under constant surveillance by sponsors and regulators. Therefore, this trial requires timely detection, evaluation, and follow-up of laboratory alterations in selected liver laboratory parameters to ensure patients' safety, see also [Section 5.2.8.1.4](#), AESIs. The implications of the current Coronavirus Disease 2019 (COVID-19) pandemic are summarized in [Section 10.4](#).

## 2. TRIAL OBJECTIVES AND ENDPOINTS

### 2.1 MAIN OBJECTIVES, PRIMARY AND SECONDARY ENDPOINTS

#### 2.1.1 Main objectives

The main objective is to investigate ocular and systemic safety and tolerability as well as disease improvement of BI 836880 after a single IVT injection and after multiple IVT injections of several doses.

#### 2.1.2 Primary endpoint(s)

SRD part:

- Number of patients with ocular dose limiting events (DLEs) from drug administration until end of trial (EOT). For definition of DLEs, refer to [Section 5.2.1](#).

MRD part:

- Number of patients with drug related AEs from drug administration until EOT.

[figure not shown]
#### 2.1.3 Secondary endpoint(s)

[figure not shown]
SRD part:

- Number of patients with drug related AEs
- Number of patients with any ocular AEs in the study eye

MRD part:

- Percent change from baseline in Central Subfield Thickness (CSFT) in the study eye at Week 12 (Visit 5), for each dose
- Change from baseline in BCVA in the study eye at Week 12 (Visit 5)
- Time to recurrence after the last treatment
- Number of patients with any ocular AEs in the study eye

### 3. DESCRIPTION OF DESIGN AND TRIAL POPULATION

#### 3.1 OVERALL TRIAL DESIGN AND PLAN

This trial will consist of an SRD part followed by an MRD part. Both parts of the trial will be conducted non-randomized, open-label, and uncontrolled.

SRD part:

The starting dose is 0.06 mg. Dose-escalation will be restricted to a maximum of 200% from the previous dose up to doses of 0.5 mg, and to a maximum of 100% from the previous dose from dose 0.5 mg onwards. The maximum planned dose is 2 mg. For any dose-escalation cohort, at least 3 patients will be required. However, in the case that only 2 patients are evaluable and neither has experienced a DLE within the evaluation period (7 days after drug administration), then dose-escalation might occur based on these 2 patients if a joint decision of the Safety Monitoring Committee (SMC), see [Section 8.7](#) is reached. Refer to [Figure 3.1: 1](#) for a schematic representation of the dose escalation. For each dose group a single patient will be dosed on day 1 in each cohort, and only after a favorable safety and tolerability assessment on day 4 the remaining 2 patients will be dosed. A Bayesian logistic regression model (BLRM), based on a weakly informative prior distribution, and employing the escalation with overdose control (EWOC) principle (see [Section 7](#)) will be used for guiding the dose escalation [[R13-4803](#)]. Cohorts of patients will receive escalating doses of BI 836880. Each cohort will consist of newly enrolled patients.

The BLM provides estimates for the probability of observing an ocular DLE for each dose level in the study as patient information becomes available. The corresponding methodology is described in [Section 7.1](#) and in [Appendix 10.3](#). At any time in the trial, it will not be permitted to escalate to a dose which does not fulfil the EWOC principle.

The maximum tolerated dose (MTD) is considered as reached if at least 6 patients have been evaluated at a dose level which is the model's recommendation for the next dose cohort. Note the MTD will likely be the highest feasible dose, 2 mg, rather than the highest tolerable dose in a strict sense.

[figure not shown]

Figure 3.1: 1 Schematic representation of the dose escalation process in the SRD part of the trial

The SMC recommends the size for the next dose escalation cohort. After all patients in a cohort have either experienced an ocular DLE or have been observed for at least the 7 days evaluation period without experiencing a DLE, the Bayesian model will be updated with the newly accumulated data. The overdose risk will then be calculated for each dose, and escalation will be permitted to all planned doses which fulfil the EWOC criterion and the respective escalation rule. As a sensitivity analysis, the BLRM might also be run again shortly before the SMC meeting, using all data available up to this time point. Based on the model results and on additional information (PK, pharmacodynamics [PD], patient profiles), the members of the SMC will reach a joint decision on the next dose level to be investigated.

If DLEs are observed in the first two consecutive patients of a previously untested dose level, subsequent enrolment to that cohort will be stopped. The BLRM will be re-run to confirm that the dose level still fulfils the EWOC principle. Based on this information, the SMC will evaluate whether the next patients will be enrolled at the same dose level, or if they will be enrolled at a lower dose level.

The SMC may decide on stopping the dose escalation after the above criterion for MTD is fulfilled. Further patients may be included to confirm that the EWOC criterion is still fulfilled.

MRD part:

The MRD part will consist of a first part (1 mg) with 11 treatment-resistant patients (cohort 1), a second part (2 mg) with 4 treatment-naïve patients (cohort 2), and approximately 12 frequently treated patients (cohort 3; inclusion criteria defined in [Section 3.3.2](#)). These are the two highest doses established by the SMC as safe and tolerable during the SRD part. Patients that had received a dose in the SRD part of the trial will not be included. In the MRD

Proprietary confidential information © 2022 Boehringer Ingelheim International GmbH or one or more of its affiliated companies

groups, patients will receive three consecutive doses over a 3-month period (once a month dosing, [Figure 3.1: 2](#)). The SMC will decide on dose escalation after 3 patients from the first MRD cohort have completed visit 5 (first follow up visit). In all patients included in the MRD parts of the trial, safety and efficacy will be studied to 12 weeks after the treatment period.

[figure not shown]

Figure 3.1: 2 Schematic representation of the dose escalation process in the MRD part of the trial

### 3.2 DISCUSSION OF TRIAL DESIGN, INCLUDING THE CHOICE OF CONTROL GROUP(S)

This trial is designed to establish a safe and effective dose for further testing in phase II trials. The trial consists of separate SRD and MRD parts. This trial will not use a placebo comparison because inclusion of a placebo arm would withhold patients with wAMD from an effective treatment for several weeks. The objectives to establish a safe and effective dose can be met without a placebo comparison.

The SRD dose escalation part is included and designed to avoid exposure of too many patients to subtherapeutic doses while on the other hand the goal of safety and rapid dose finding is preserved. This part of the trial will already be done in patients because IVT injections in healthy subjects would not be considered appropriate. Dose escalation and cohort size will be decided by the SMC, guided by a BLRM with overdose control. An EWOC design will increase the chance of treating patients at efficacious doses while

reducing the risk of overdosing. The use of Bayesian models for Phase I studies has also been advocated by the European Medicines Agency (EMA) guideline on small populations [R07-4856] and by the Food and Drug Administration (FDA) [R13-4881].

It is expected that, in the study population of patients not sufficiently responding to anti-VEGF treatment, a reduction of fluid in the retina should be observed only after multiple treatments. Therefore, two MRD cohorts (3 injections in a monthly interval) will be included after the SRD part. This part of the trial will generate additional safety data after multiple dosing and allow for exploration of the time course and durability of treatment effects. These data will further support the definition of the injection frequency and intervals in later studies.

### 3.3 SELECTION OF TRIAL POPULATION

This trial will recruit up to 18 patients in the SRD part (the SRD part was completed with 15 patients) and up to 27 patients in the MRD part (cohort 1, 2 and 3). Please refer to [Section 7.7](#) for details and justification.

Screening of patients for this trial is competitive, i.e. screening for the trial will stop at all sites at the same time once a sufficient number of patients has been screened. Investigators will be notified about screening completion and will then not be allowed to screen additional patients for this trial.

A log of all subjects enrolled into the trial (i.e. who have signed informed consent) will be maintained in the Investigator Site File (ISF) at the investigational site irrespective of whether they have been treated with investigational drug or not.

#### 3.3.1 Main diagnosis for trial entry

This study enrolls patients with subfoveal choroidal neovascularization secondary to wAMD that have insufficiently responded to previous anti-VEGF therapies who meet all inclusion criteria and do not meet any exclusion criterion.

Please refer to [Section 8.3.1](#) (Source Documents) for the documentation requirements pertaining to the in- and exclusion criteria.

#### 3.3.2 Inclusion criteria

##### SRD part and MRD cohort 1 (treatment-resistant patients with wAMD):

1. Men and women over the age of 55 with active CNV secondary to AMD despite anti-VEGF therapies (at least 3 prior injections with the last injection within 16 to 4 weeks before treatment). Active CNV secondary to AMD is to be defined either by recent fluorescein or OCT angiogram within 4 weeks prior to screening or fluorescein or OCT angiogram obtained prior to first anti VEGF-treatment to confirm the diagnosis and still active according to investigator judgement.
2. Deleted.
3. For MRD part only: Central subfield retinal thickness >300 microns in the study eye on Heidelberg Spectralis Spectral Domain Optical Coherence Tomography (SD-OCT).
4. Presence of sub- and/or intraretinal fluid on SD-OCT in the study eye.
5. Any active CNV with subfoveal leakage in the study eye as determined by OCT
6. No subretinal hemorrhage involving the fovea in the study eye.

Proprietary confidential information © 2022 Boehringer Ingelheim International GmbH or one or more of its affiliated companies

7. No significant subfoveal fibrosis or atrophy on SD-OCT in the study eye that, in the opinion of the investigator, is able to prevent improvement in BCVA and/or CSFT.
8. Best-corrected Early Treatment Diabetic Retinopathy Study (ETDRS) VA in the study eye between 75 and 24 letters inclusive (approximately 20/32 and 20/320 or 6/9.5 and 6/95) at screening.
9. Best-corrected VA in the non-study eye better than best-corrected VA in the study-eye. If both eyes are eligible and have identical VA the investigator may select the study eye.
10. Male or female patients. Women of childbearing potential (WOCBP) cannot be included. Men able to father a child must be ready and able to use highly effective methods of birth control per ICH M3 (R2) that result in a low failure rate of less than 1% per year when used consistently and correctly. A list of contraception methods meeting these criteria is provided in the patient information and in [Section 4.2.1.3](#).
11. Signed informed consent consistent with ICH GCP guidelines and local legislation prior to participation in the trial, which includes medication washout and restrictions.
12. Not under any administrative or legal supervision or under institutionalization due to regulatory or juridical order.

MRD cohort 2 (treatment-naïve patients with wAMD):

1. Not applicable: Adapted to inclusion criterion #13, see below.
2. Not applicable: Deleted.
3. Not applicable: No limitation on central subfield retinal thickness.
4. Not applicable: Adapted to inclusion criterion #14, see below.
5. Not applicable: Adapted to inclusion criterion #14, see below.
6. No subretinal hemorrhage involving the fovea in the study eye.
7. No significant subfoveal fibrosis or atrophy on SD-OCT in the study eye that, in the opinion of the investigator, is able to prevent improvement in BCVA and/or CSFT.
8. Not applicable: Adapted to inclusion criterion #15, see below.
9. Not applicable: Adapted to inclusion criteria #16 and #17, see below.
10. Male or female patients. Women of childbearing potential (WOCBP) cannot be included. Men able to father a child must be ready and able to use highly effective methods of birth control per ICH M3 (R2) that result in a low failure rate of less than 1% per year when used consistently and correctly. A list of contraception methods meeting these criteria is provided in the patient information and in [Section 4.2.1.3](#).
11. Signed informed consent consistent with ICH GCP guidelines and local legislation prior to participation in the trial, which includes medication washout and restrictions.
12. Not under any administrative or legal supervision or under institutionalization due to regulatory or juridical order.
13. Men and women over the age of 55 with treatment-naïve CNV secondary to AMD.
14. Any CNV with subfoveal activity in the study eye defined as evidence of sub- and/or intraretinal fluid, or subretinal hyper-reflective material, or angiographic leakage.
15. Best-corrected Early Treatment Diabetic Retinopathy Study (ETDRS) VA in the study eye between 80 and 24 letters inclusive (approximately 20/25 and 20/320 or 6/7.5 and 6/95) at screening.
16. Best-corrected ETDRS VA in the non-study eye 50 letters inclusive (approximately 20/100 or 6/30) or better at screening.
17. If both eyes are eligible at screening, the study eye is the eye with the worse best-corrected VA.

**MRD cohort 3 (frequently treated patients):**

- 1-5. Not applicable to cohort 3.
6. No subretinal hemorrhage involving the fovea in the study eye.
7. No significant subfoveal fibrosis or atrophy on SD-OCT in the study eye that, in the opinion of the investigator and with the endorsement of the Sponsor, is able to prevent improvement in BCVA.
- 8-9. Not applicable to cohort 3.
10. Male or female patients. Women of childbearing potential (WOCBP) cannot be included. Men able to father a child must be ready and able to use highly effective methods of birth control per ICH M3 (R2) that result in a low failure rate of less than 1% per year when used consistently and correctly. A list of contraception methods meeting these criteria is provided in the patient information and in [Section 4.2.1.3](#).
11. Signed informed consent consistent with ICH GCP guidelines and local legislation prior to participation in the trial, which includes medication washout and restrictions.
12. Not under any administrative or legal supervision or under institutionalization due to regulatory or juridical order.
13. Not applicable to cohort 3.
14. Any CNV with subfoveal activity in the study eye defined as evidence of sub- and/or intraretinal fluid, or subretinal hyper-reflective material, or angiographic leakage.
15. Best-corrected Early Treatment Diabetic Retinopathy Study (ETDRS) VA in the study eye between 80 and 24 letters inclusive (approximately 20/25 and 20/320 or 6/7.5 and 6/95) at screening.
16. Not applicable to cohort 3.
17. If both eyes are eligible at screening, the study eye is the eye with the worse best-corrected VA.
18. Men and women over the age of 55 with diagnosed wAMD that:
  - require frequent wAMD SoC (28-56 days between the last 3 treatments)
  - have had  $\geq 3$  previous treatments with IVT SoC (ranibizumab, aflibercept, or bevacizumab) in the study eye
  - had the last SoC injection  $\geq 4$  weeks, but no more than 8 weeks, before the first administration of the study drug
  - have been on SoC treatment  $\geq 6$  months and are within 3 years from initial wAMD diagnosis in the study eye

 A woman is considered of childbearing potential (WOCBP), i.e. fertile, following menarche and until becoming postmenopausal unless permanently sterile. Permanent sterilisation methods include hysterectomy, bilateral salpingectomy and bilateral oophorectomy. Tubal ligation is NOT a method of permanent sterilisation. A postmenopausal state is defined as no menses for 2 years without an alternative medical cause. A high follicle stimulating hormone (FSH) level in the postmenopausal range may be used to confirm a post-menopausal state in women not using hormonal contraception or hormonal replacement therapy. However, in the absence of 2 years of amenorrhea, a single FSH measurement is insufficient.

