## 5. ASSESSMENTS

### 5.1 ASSESSMENT OF EFFICACY

For the endpoints, baseline is defined as the value at Visit 2; if not measured at Visit 2 then baseline is the value at Visit 1. All ophthalmologic examinations will be performed on both eyes, as described below.

Centrally collected ophthalmological data (CFP, OCT/OCT-A) will be transferred from the Central Reading Center (CRC) to the sponsor's database. The local measurement data will remain at the study sites as source documents.

If clinically significant worsening is observed in the assessments of efficacy during the study, it will be reported as AE in the eCRF (please also refer to [Section 5.2.8](#)).

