6.7 BASELINE, TIME WINDOWS AND CALCULATED VISITS

The baseline value is defined as the last measurement before first administration of BI 836880 (= value at V2, in case no actual time is given in data).

Section 5.1 of the CTP: *For the endpoints, baseline is defined as the value at Visit 2; if not measured at Visit 2 then baseline is the value at Visit 1.*

The acceptable time windows for visits are given in the CTP Flow Chart.

Adherence to time windows will be checked via the consistency check listings at the MQRM/RPM/DBLM.

To utilize all available data, including values collected between protocol-specified visit windows and unscheduled visits, time intervals will be defined for analysis of efficacy data. If multiple values are recorded within a visit interval, the value collected closest to the planned visit date will be included in analyses of efficacy endpoints (CSFT, BCVA, and responder analysis) and IOP.

Unscheduled measurements of laboratory data and vital signs data will be assumed to be repeat measurements of the most recent scheduled measurement (e.g. for follow-up or confirmation of a particular value). Therefore, unscheduled measurements will be assigned to the planned time point of the previous scheduled measurement.

Table 6.7: 1 Visit intervals for efficacy endpoints (CSFT, BCVA, responder analysis) and IOP

| Visit | Planned day | Interval Definition | | Visit description |
|--------------|--------------------|----------------------------|----------------------|--------------------------|
| | | From (day) | To (day) | |
| 1 | -28 to -3 | NA | -1 | Screening |
| 2 | 1 | 1 | 1 | Baseline |
| 3 | 29 | 2 | 43 | Week 4 |
| 4 | 57 | 44 | 71 | Week 8 |
| 5 | 85 | 72 | 99 | Week 12 |
| 6 | 113 | 100 | 127 | Week 16 |
| 7 | 141 | 128 | 155 | Week 20 |
| 8 | 169 | 156 | Last assessment date | Week 24 |

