7.5.2 Secondary objective analysis

Section 7.3.2 of the CTP:

In principle, all secondary endpoints specified in [Section 5.2.2](#) will be analyzed descriptively, based on the TS. The analysis of percent change from baseline in CSFT in the study eye at week 12 (Visit 5) will be done by dose, based on the FAS.

Descriptive statistics for absolute values as well as changes from baseline (percent changes and changes in CSFT and changes in BCVA (study eye)) will be provided by dose group/cohort and in total. Time profiles of mean (\pm SD) absolute values and mean (\pm SD) changes from baseline by cohort as well as individual time profiles (absolute values and changes from baseline) per treatment group/cohort will be provided. For percent changes of CSFT, median and minimum/maximum values will be shown instead.

For those endpoints related to adverse events refer to [Section 7.8.1](#).

Section 5.2.2 of the CTP:

Time to recurrence will be assessed in the MRD part, based on the TS, from last trial drug administration to occurrence of any of the following in the study eye, leading to the use of wAMD rescue medication as decided by the investigator:

- *Increase in CSFT $\geq 75 \mu\text{m}$ with a decrease in BCVA of ≥ 5 letters compared to Visit 5, OR*
- *Decrease in BCVA of > 5 letters compared to baseline (Visit 2), due to worsening wAMD activity,*
OR
- *Decrease in BCVA of ≥ 10 letters compared to the best prior BCVA, due to worsening wAMD activity*

From above criteria, if Visit 5 BCVA/CSFT assessment data is missing, BCVA/CSFT values available earlier than Visit 5 will be used. The last trial drug administration is strictly referring to the third injection, if a patient doesn't complete three injections, the patient will not be evaluated for time to recurrence endpoint and will be censored as per [Table 7.5.2:1](#). The details of censoring rules are listed in the [table](#) below. Kaplan-Meier curves will be estimated by cohort.

Table 7.5.2: 1 Censoring Rules for time to recurrence

| No. | Scenario | Relative Day of Event or Censoring | Outcome |
|-----|--|---|--------------------|
| 1 | A patient meets more than one recurrence rule | Earliest day of recurrence | Event (Recurrence) |
| 2 | A patient completed the treatment and follow-up without recurrence | Last day of follow-up | Censored |
| 3. | SAE after completion of three injection | Day of SAE | Censored |

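### In MRD cohorts 1 and 3, baseline CSFT and BCVA can fall later in the injection cycle than Week 12, so part of the Week 12 change can reflect a shorter time since injection

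*Protocol*

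**What the plan says.** **Entry.** Protocol 3.3.2, cohort 3 criterion 18, requires the last SoC injection at least 4 weeks, "but no more than 8 weeks, before the first administration of the study drug", in patients with "28-56 days between the last 3 treatments". For cohort 1, criterion 1 requires "at least 3 prior injections with the last injection within 16 to 4 weeks before treatment".

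**Baseline.** Protocol 5.1: "baseline is defined as the value at Visit 2; if not measured at Visit 2 then baseline is the value at Visit 1". SAP 6.7: "The baseline value is defined as the last measurement before first administration of BI 836880".

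**Week 12.** Flow Charts II and IV put Visit 5 on Day 85. Protocol Table 4.1.4: 2 puts the three doses on Days 1, 29 and 57. Protocol 1.4 describes Visit 5 as 4 weeks after the third injection.

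**Analysis.** SAP 7.5.2: "The analysis of percent change from baseline in CSFT in the study eye at week 12 (Visit 5) will be done by dose", on the FAS. CSFT and BCVA changes are summarised descriptively by dose group/cohort and in total. The visible SAP has no subgroup, adjustment or display by time since the last anti-VEGF injection.

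**Design.** Both parts are uncontrolled (Protocol 3.1). Section 3.2 argues against a placebo arm and does not discuss the change in injection interval at entry.

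**The concern.** Change from baseline compares two points in an injection cycle. After dosing, the plan fixes that point at about 4 weeks since the last injection. Before dosing, it lets the point range from 4 to 8 weeks (cohort 3) or 4 to 16 weeks (cohort 1).

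The earlier drugs are themselves active: Protocol 1.3 calls anti-VEGF treatment effective and quick to act. If retinal fluid builds up as such an injection wears off, a patient measured 8 weeks after SoC and again 4 weeks after BI 836880 could look better merely because the second measurement is closer to an injection. A drug no better than the earlier one could show the same.

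At stake is the reading of two secondary endpoints, CSFT and BCVA change at Week 12. These data are used: Protocol 1.3 cites interim findings, including CSFT, as the reason for adding cohort 3. Cohort 2 is treatment-naïve and is not affected.

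**Working it through.** **1. Days since the last injection (nominal schedule)**

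| | Baseline | Week 12 | Baseline later by |
|---|---|---|---|
| Cohort 3 | 28 to 56 | 85 − 57 = 28 | 0 to 28 days |
| Cohort 1 | 28 to 112 | 85 − 57 = 28 | 0 to 84 days |

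The lower entry limit equals the nominal Week 12 interval, so the nominal difference is never negative. If entry intervals were spread evenly (assumption), the mean excess would be (28 + 56)/2 − 28 = 14 days in cohort 3 and (28 + 112)/2 − 28 = 42 days in cohort 1.

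**2. How far the actual interval can vary**

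- With ±3 days on both visits: (85 − 3) − (57 + 3) = 22 to (85 + 3) − (57 − 3) = 34 days.
- With the SAP Table 6.7: 1 interval (Days 72 to 99) and the third dose on Day 57: 15 to 42 days.
- The FAS requires only one dose, so some patients may have no third dose.
- If the Visit 1 value serves as baseline, the baseline interval is shorter.

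The one-sided direction is therefore a property of the schedule, not of every patient.

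**3. Week 16 for comparison.** Visit 6 is 113 − 57 = 56 days after the third dose, equal to or longer than every permitted cohort 3 baseline interval. The nominal bias cannot run in the drug's favour there.

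**4. The plan's own figures.** Protocol Table 7.7: 1 takes a normal percent decrease with SD 16 and gives the chance that the observed median is at least 20%. Simulating the median (1,000,000 trials per row) for true decreases of 13 / 19 / 25% gives:

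- N=10: 12.0 / 43.3 / 80.0 (table: 11.9 / 43.3 / 80.1)
- N=15: 8.5 / 42.2 / 83.7 (table: 8.6 / 42.2 / 83.7)

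The table is reproduced.

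**5. What an artefact would do to those figures.** The documents give no size, so these are assumed shifts. Each is added to a true decrease of 13%; entries are P(observed median ≥ 20%) in percent.

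| Shift (points) | 0 | 3 | 6 | 9 | 12 |
|---|---|---|---|---|---|
| N=10 | 12.0 | 25.0 | 43.3 | 63.3 | 80.0 |
| N=11 (cohort 1) | 11.8 | 25.0 | 43.3 | 63.2 | 80.1 |
| N=12 (cohort 3) | 10.1 | 23.2 | 42.7 | 64.3 | 81.9 |

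With no true effect, a 12-point shift gives 8.9% (N=10) and 7.2% (N=12).

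**6. Same check with intervals that differ between patients.** Assume evenly spread intervals and an artefact proportional to the excess days.

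| Cohort | Points per excess day | Mean shift | P(≥ 20%), true 13% | P(≥ 20%), true 0% |
|---|---|---|---|---|
| 3 (N=12) | 0.1 | 1.4 | 15.4 | 0.0 |
| | 0.2 | 2.8 | 22.2 | 0.1 |
| | 0.3 | 4.2 | 30.6 | 0.2 |
| 1 (N=11) | 0.1 | 4.2 | 32.1 | 0.4 |
| | 0.2 | 8.4 | 58.9 | 3.1 |
| | 0.3 | 12.6 | 80.5 | 13.0 |

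Under these assumptions a weak effect can look stronger, more so in cohort 1. An artefact with no true effect behind it seldom reaches 20%.

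**The case against.** The strongest reply is that this is an exploratory, descriptive phase I/IIa trial. Its primary endpoints are safety endpoints, no hypothesis is tested, and the lack of a control is openly declared. All of that is right and limits the weight of the point.

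A reader might infer that change from baseline is the only efficacy evidence. It is not. Time to recurrence is a secondary endpoint (SAP 7.5.2), and cohort 3 has a Week 16 responder endpoint (SAP 4). The latter does not share this direction of bias, but it is binary, covers one cohort, and does not correct Week 12 CSFT or BCVA.

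A reader might also infer that the interval alone could reach the 18% and 20% cut-offs of Table 7.7: 1. That turns a patient-level rise into a group median. Suppose CSFT at day 56 were 10% to 30% above its day-28 value. A patient at day 56 would show 1/1.10 − 1 = −9.1% to 1/1.30 − 1 = −23.1%. With a linear rise and evenly spread intervals, the middle patient sits at day 42 and shows 1/1.05 − 1 = −4.8% to 1/1.15 − 1 = −13.0%, short of both cut-offs. No document supports any of these rises, no visible decision rule uses the cut-offs, and Protocol 7.7 makes no formal calculation for cohort 3.

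A third inference is that cohort 1 patients with a long gap are lapsed rather than resistant. Criterion 1 requires active disease despite at least three injections, and nothing in the documents supports a split at 8 weeks.

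Much of the raw material is already planned: mean and individual profiles over time (SAP 7.5.2), listings by visit (SAP 7) and previous therapies by cohort (SAP 7.2). What is missing is the variable that links them. Some protocol and SAP text is redacted, so its absence is judged on the visible text.

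**Conclusion.** The point holds in a limited form. In cohorts 1 and 3, part of the Week 12 change in CSFT and BCVA can come from a shorter time since injection, and the planned cohort-level summaries cannot show how much. The nominal mismatch is 0 to 84 days in cohort 1 and 0 to 28 days in cohort 3, in a direction that favours apparent improvement. Patients entering at 28 days have no nominal mismatch, so the effect on a cohort depends on its mix of intervals.

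The size cannot be estimated from the documents. The simulated figures rest on assumed shifts, SD 16, normality and, where stated, evenly spread intervals. They show sensitivity and do not predict a bias.

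The documents do not support saying that the artefact alone would produce the result the sponsor hopes for, or that the trial has no other efficacy evidence. The safety objectives are untouched. This is a worthwhile SAP addition to secondary endpoints.

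**What to change.** Keep the Week 12 endpoints and add to SAP 7.5.2:

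1. **Derived variable.** Days from the last study-eye anti-VEGF injection to the measurement used as baseline, tabulated for cohorts 1 and 3.
2. **Display.** Week 12 CSFT and BCVA change plotted or listed against that variable, by cohort.
3. **Cohort 3 only.** Beside Week 12, a within-patient change at whichever of Visit 5 (28 days) or Visit 6 (56 days) is closer to the patient's baseline interval. Use values before any study-eye SoC, and state how many patients are excluded for SoC. Fix a rule for the tie at 42 days. The nominal mismatch left is then at most 14 days and no longer runs one way.
4. **Cohort 1.** Stop at the plot or listing. Protocol 4.2.1.1 leaves SoC to the investigator's discretion from Visit 5, so matching at Visits 7 and 8 would select patients who did not need re-treatment.

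If the data have already been examined, label the additions post hoc.

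**Cost.** SAP wording, one variable and a few displays. The injection date is already needed for eligibility, and the OCT and BCVA visits already exist. The numbers are small (11 and about 12 patients). Matching leaves dosing intensity confounded, since three monthly doses are compared with a possibly less frequent regimen. The result may look less favourable.
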